3.3 BLINDING

Due to the nature of the intervention, involved caregivers and participants will not be blinded. In addition, the person of the study team who reviews the diaries and verifies the correct performance of study-related procedures by nurses is also not blinded. Because the diaries provide information about assignment to the study arm, blinding of the reviewer is not possible due to the given circumstances. In order to enhance the internal validity, every visit will be performed by two members of the study team.

Member 1 of the study team performs the following tasks:

- (I) Conduct of the study visit and its related tasks as listed in Table 3 under the section "Clinical skin assessment" (including assessment of IAD-related pain, itch, patient satisfaction as well as the instrumental measurement of the erythema). Member 1 **does not conduct** any part of the assessment regarding the condition of the skin, which includes GLOBIAD IAD categorization as well as the visual inspection of erythema, erosion and maceration.
- (II) Conduct of monitoring activities as described in Table 1 under the section "11. How well".

Member 2 ("outcome assessor") of the study team is blinded and does the skin condition-related assessments only (including GLOBIAD IAD categorization as well as the visual inspection of erythema, erosion and maceration). The blinded person documents the results of the skin assessment on a separate "Skin Assessment Data Collection Form" (see **Fehler! Verweisquelle konnte nicht gefunden werden.**), independently from the main CRF (see **Fehler! Verweisquelle konnte nicht gefunden werden.**). This procedure is necessary to prevent accidental unblinding of the outcome assessor by trial group-specific information collected in the main CRF. The Skin Assessment Forms will be reintegrated into the main CRF after the respective participant has completed the study or ended its participation.

The data manager will be blinded throughout the period of data entry and verification until data base closure. The trial statistician will be blinded during statistical analysis.

4. METHODS: DATA COLLECTION, MANAGEMENT, AND ANALYSIS

4.1 DATA COLLECTION METHODS

All data collectors will be trained in obtaining accurately the variables of interest (see 2.7 and 4.1.3). Paper source data (SD) and paper case report forms (CRFs) will be used to document all study variables of interest. SDs will include originals/copies/transcripts of resident-/patient-related records, physicians', nurses' and research assistants' notes, visit schedules, diaries, dispensing LOGS, signed ICFs other relevant reports.

All examinations, assessments, and measurements will be performed onsite in the participating geriatric hospitals/wards and nursing homes in the patients'/residents' room. Demographic characteristics and basic medical information such as main medical diagnoses and regular medication will be extracted from the master data records of the respective institutions. The skin assessments will be performed by an experienced and qualified member of the study team who, as a blinded outcome assessor, will be constantly vigilant to avoid accidental unblinding. Other assessments and the skin measurements will be conducted by trained members of the study team, which are not involved in the skin condition assessments (including GLOBIAD IAD categorization and visual inspection of erythema, erosion and maceration).

All study data has to be continuously documented in the CRFs and associated forms by the investigator or his authorized staff. Data entries have to be made by using a non-erasable blue or black ballpoint pen. Data corrections must be made in a way which does not obscure the original entry. The corrected data must be dated and initialed by the corrector. Predefined variables will be

entered into an eCRF provided by the CTO of the Charité meeting GCP standards (including personalized login and track change).

4.1.1 SKIN ASSESSMENT

The skin assessments visits will be performed at Days 0, 2, 4, 6, 8, 10, 12 and 14. This will be performed by GCP-trained members of the study team. Nursing home residents/patients in geriatric hospitals/wards will be assisted to undress at the area of interest. In close cooperation with the caregivers, this will be ideally combined with the scheduled regular general basic care procedures, clothing changes or medical procedures.

The variables regarding IAD categorization, erythema, erosion and maceration will be documented by the blinded assessor. In case that a dermatological/medical condition is detected which is, in the opinion of the assessor, incompatible with further study conduct, participation for this subject will be terminated with specification of the underlying reason

4.1.2 SKIN MEASUREMENTS

Erythema level measurements will be conducted at Days 0, 2, 4, 6, 8, 10, 12 and 14 in duplicates at the cranial end of the gluteal cleft. Study team members will conduct the measurements according manufacturer's instruction manual (**Fehler! Verweisquelle konnte nicht gefunden werden.;** **Fehler! Verweisquelle konnte nicht gefunden werden.**) and the respective SOP (see **Fehler! Verweisquelle konnte nicht gefunden werden.**). All study team members who perform the measurements will have a documented training prior to the study and undergo a brief examination to ensure similar measurement performance. Used measurement devices will be calibrated and serviced periodically according to the manufacturer instructions.

4.1.3 OTHER TRIAL DATA

Other collected trial data are shown in-Table 4.

Table 4: Other trial data

Variable Name	Device/Measurement instrument/Scale and metric	Time points	Response Options/Categories/Range
Demographics			
Age	
 Age in years 	Day 0	XXX [years; numeric]
Sex	
 Obtained from medical record 	Day 0	(1) Male (2) Female
Care level	
 Obtained from medical record in nursing homes According to Volume XII of the German Social Security Code (SGB XII), defined by § 61b SGB XII 	Day 0	(1) none; (2) Grade 1 (3) Grade 2 (4) Grade 3 (5) Grade 4 (6) Grade 5
Smoking status	
 Smoking status according to participant's statement 	Day 0	
 Smoking status: (1) Smoker (2) Non-smoker
Body height	
 Obtained from medical record Height in cm 	Day 0	XXX [numeric]
Body weight	
 Obtained from medical record Weight in kg 	Day 0	XXX [numeric]
BMI	
 Calculated from body weight and body height BMI = kg/m² 		XX [numeric]
Skin phototype	
 According to Fitzpatrick classification 	Day 0	(1) Skin Type I; (2) Skin Type II; (3) Skin Type III; (4) Skin Type IV; (5) Skin Type V; (6) Skin Type VI
Medical History/ Functional Assessments			
Main medical diagnoses	
 Relevant main diagnoses obtained from medical records 	Day 0	
 Main medical diagnosis 
 Hypertension Dementia Renal failure Diabetes mellitus Heart arrhythmia

Medications	
 Relevant medications obtained from medical records 	Day 0	
 Category of medication (1) Antithrombotic medication (2) Beta-adrenoreceptor antagonists (3) Diuretics (4) Medication influencing the renin-angiotensin (5) Psychoanaleptics (6) Antibiotics
Cognitive Ability	
 Assessed with the MMSE Score range: 0 to 30 	Day 0	
 (1) ≥ 24 (Normal cognition; no dementia) (2) 19 to 23 (Mild dementia) (3) 10 to 18 (Moderate dementia) (4) 9 and lower (Severe dementia)
Physical function	
 Barthel – Index Score range: 0 to 100 Means 	Day 0	
 Item 1: Feeding (0; 5 or 10 points) Item 2: Bathing (0 or 5 points) Item 3: Personal toilet (0 or 5 points) Item 4: Dressing and undressing (0; 5 or 10 points) Item 5: Controlling bowels (0; 5 or 10 points) Item 6: Controlling bladder (0; 5 or 10 points) Item 7: Toilet use (0; 5 or 10 points) Item 8: Transfer (bed to chair and back) (0; 5; 10 or 15 points) Item 9: Standing up and Mobility (0; 5; 10 or 15 points) Item 10: Ascend and descend stairs (0; 5 or 10 points)
Diarrhoea	
 Interview by study assistant or obtained from medical records 	Day 0	
 Diarrhoea (0) No (1) Yes
Urinary tract infection	
 Interview by study assistant or obtained from medical records 	Day 0	
 Urinary tract infection (0) No (1) Yes

Demographic variables (age, sex, care level,), main medical diseases, medications and, if possible, Barthel-Index scores will be obtained from medical records by trained study assistants. Data regarding incontinence will be obtained from the medical records or if possible via interview of the participants or the responsible caregiver.

A possible cognitive impairment will be rated using the MMSE [29]. Only residents with a score of 24 or higher will receive the questionnaires regarding itch, pain and patient satisfaction. A functional assessment using the Barthel-Index will be conducted by study assistants, if this has not already been done by the nursing home. The Barthel-Index measures physical function related to the daily activities using ten items (e.g. washing and toilet use, eating and mobility or incontinence). Scores ranges from 0 (= very dependent) to 100 (= not dependent) [38].

4.2 DATA MANAGEMENT

A paper SD file will be created for the study. Data (informed consent process and consent retrieval, demographics, medical history, skin assessments, skin measurements, clinical scores, rating scales) will be collected during the study visits in written form. An eCRF will be developed by the CTO. Data from the SD will be extracted and entered into an eCRF. The investigator agrees to maintain accurate CRF and source documentation as part of the research under this protocol. Data management and handling of data will be conducted according to the trial specific Data Management Plan (DMP) of the CTO in accordance with ICH guidelines.

Data entry will be performed by the trial site personnel. Validation and data queries will be handled by the data management team of the study. According to a pre-defined query process changes to data entries in the eCRF (if any) will be made at the site by the qualified trial site personnel. The eCRF will have an audit trail with appropriate functionality for data capture, tracking and documentation of any queries or changes. Electronic signatures will be used to verify the data and identify the person entering or changing the data (SecuTrial).

After all data management activities (query and cleaning process) are completed, the database will be locked and exported as SPSS datasets. Any deviations, i.e. discrepancies and additions from the process defined in the DMP, will be described in a trial specific data management report.

4.3 STATISTICAL METHODS

All statistical evaluations will be conducted using the statistical programming language R and IBM SPSS statistics.

Variables will be described for each setting (geriatric hospitals/hospital wards and nursing homes) and individual level on an intention-to-treat (ITT) basis. Outcomes will be described using means, medians, proportions (including the cumulative incidence) and corresponding spread estimates per group. Mean differences between groups and time points will be calculated. In addition, we will provide Kaplan-Meier curves for the time from inclusion in the study to the onset of IAD in the three study groups. The observations are censored if patients withdraw from the study before the onset of an IAD or if the study is terminated before the onset of an IAD. Because this is an exploratory trial no group comparisons using formal statistical tests will be performed. However, we will calculate two-sided 95% confidence intervals for all means and proportions and for the differences in means and proportions between the three study groups. All statistical analyses will be performed for the whole sample and for both sex strata separately.

The interviews and free text responses will be analyzed using qualitative methods including labelling, coding, and inductive outcome extraction.

4.4 ANALYSIS POPULATION

The statistical analysis will be based on the ITT principle, this includes the whole study population and is considered as the 'full analysis set'. The IIT analysis bases on the initial treatment intent. The analysis contains all participants that met the inclusion criteria and were randomized, irrespective of possible protocol deviations, discontinuation of the study treatment or withdrawal from the study by the subject. Participants that die, discontinue participation or leave the institution during the study period will be analyzed until that time point (early termination). As only exception, the following reasons cause an exclusion of participants from the full analysis set: (I) No treatment was applied at all or (II) there are no data available after the subject's randomization. Subjects excluded from the full analysis set will be mentioned in the study report and reasons for exclusion will be documented per group. In case of consent withdrawal, all subject's data collected until this time point will remain part of the study database and may not be removed. This will be clearly stated in the ICF.

An additional per protocol (PP) analysis will be performed. The parameters for inclusion in the PP analysis set are defined as follows: **(I)** Participants that completed the study without major protocol deviations or violations (i. e. wrong product/incorrect application, missing application for more than 72 h, more than three missing study visits, inclusion/exclusion criteria not met) and **(II)** terminated the study regularly (study participation of at least 7 consecutive days). For all subjects included in the full analysis set but not in the PP set, the reason for exclusion will be stated in the

study report per group. As the ITT analysis is intended to preserve the original randomization and to avoid potential bias due to exclusion, the PP analysis aims to analyze the possible effects of the intervention administered under optimal conditions. Therefore, both analyzes are a necessary component to determine the feasibility of the applied procedures as well as possible effects of the intervention. Especially with regard to planning of a subsequent confirmatory trial.

5. METHODS: MONITORING

5.1 DATA MONITORING

A clinical trial advisory board (CTAB) will be implemented. It consists of national and international experts in the field of dermatology, geriatrics and nursing science. Further, representatives of the German Incontinence Support Group (Deutsche Inkontinenz Selbsthilfe e.V.) will be part of the CTAB, representing the interests of the nursing home residents and patients. The support group will invite incontinent patients to be part of the study committee. A meeting will be held in which the background and aims of the study were presented and the general aspects of the planning, implementation and analysis of the study were explained. The CTAB will then actively participate in full clinical trial protocol development, review and supervision of the study progress.

Monitoring of the study is the responsibility of the Investigator and is delegated to CTO. The monitor is responsible for reviewing the progress of the study, verifies the adherence to the protocol as well as compliance to ICH-GCP. The monitor works according to the SOPs of the CTO. The monitor will visit the center before, during, and after completion of the study to ensure that the study is conducted, recorded, and reported according to the protocol. During the on-site visits, parts of the eCRF will be reviewed for completeness with corresponding SDs. As part of the data audit, SDs will be made available for review by the study monitor. The study monitor may periodically request review of the ISF to ensure completeness of documentation in all respects of study conduct. The monitor may verify the participation of an institution via phone call with the responsible contact person of the nursing home/ hospital/ hospital ward.

5.2 ELECTRONIC DATA CAPTURE

Data entry

The CTO uses secuTrial® - a Remote Data Entry (RDE) software solution of interActive Systems (iAS) - to capture trial data and transfer them to a central database. SecuTrial® is in compliance with the regulatory standards (FDA CFR 21 Part 11 and GCP) and contains the required features like audit trail, assigned roles and rights of study employees, management concept and electronic signatures.

The system provides the eCRF which allows the documentation of trial data online at any time by using a standard internet browser (e.g. Chrome, Firefox, Opera, etc.). Furthermore the eCRF contains functions to perform plausibility, consistency and range checks of the entered data to get a high level of data quality. Access to the eCRF is person-specific and password protected. All access rights (read or enter data) will be defined depending on their function in the trial (principle or clinical investigator, study assistant etc.).

The communication between the client-PC and the trial database on the server is based on the secure data-transfer-protocol (SSL - Secure Sockets Layer). This will prevent any illegal access to the trial data by unauthorized parties.

Query Management

There is a Query management tool as an integrated part of the RDE system. This tool allows the communication between the CTO and the clinical investigator at the site. In case of uncertainties, errors or improper data, the CTO or the monitor can set queries to clarify the affected question.

5.3 HARMS

One investigational product for skin protection is 'ESENTA™ Hautschutz Spray' (PZN: 16866747). It is CE certified in accordance with Article 20 (1) of Regulation (EU) 2017/745. The investigational product is used and evaluated within its defined intended purpose in the context of the planned clinical trial. Therefore, its use is considered safe and the use of the investigational product does not impose any additional burden on the participants. The other product used for skin protection is 'Hydrophobes Basisgel DAC'. It may be regarded as a cosmetic product according to the EU Regulation No 1223/2009 on cosmetic products.

5.3.1 DEFINITION OF ADVERSE EVENTS AND INCIDENTS

Long-term care residents and patients in acute care are affected by a variety of diseases and medical problems. Therefore, the Adverse Events (AEs) and Serious Adverse Events (SAEs) terminology (according to EU regulation 2017/745 MDR Article 2 (57) and (58)) will be adopted for this trial.

Adverse Event

An AE is any untoward medical occurrence, unintended disease or injury or any untoward clinical signs, including an abnormal laboratory finding, in subjects, users or other persons, in the context of the clinical investigation, and is related to the investigational device.

The observation period for AEs begins at the time the resident/patient gives informed consent and continues until the study is completed. All residents experiencing AEs will be monitored

until symptoms subside, or until there is a satisfactory explanation for the changes observed. If the interval between two episodes of an AE is less than seven days, these episodes will be counted as one AE.

The investigator will be responsible for the necessary acute medical treatment of any adverse event that occurs during the trial and that is related to the investigational product. The investigator ensures that appropriate medical care is also provided thereafter, if necessary.

Serious Adverse Event

Serious Adverse Event (SAE) means any AE that led to any of the following:

- (a) death,
- (b) serious deterioration in the health of the subject, that resulted in any of the following:
 - (i) life-threatening illness or injury,
 - (ii) permanent impairment of a body structure or a body function,
 - (iii) hospitalization or prolongation of patient hospitalization,
 - (iv) medical or surgical intervention to prevent life-threatening illness or injury or permanent impairment to a body structure or a body function,
 - (v) chronic disease

Hospitalization solely for the purpose of diagnostic tests, even if related to an AE, elective hospitalization for an intervention which was already planned before the inclusion of the resident in the clinical study, and admission to a day-care facility may not themselves constitute sufficient reasons to be considered as a SAE.

Incident

"An 'incident' means any malfunction or deterioration in the characteristics or performance of a device made available on the market, including use-error due to ergonomic features, as well as any inadequacy in the information supplied by the manufacturer and any undesirable side-effect" (EU regulation 2017/745 MDR Article 2 (64))

Serious Incident

"A 'serious incident' means any incident that directly or indirectly led, might have led or might lead to any of the following:

- (a) The death of a patient, user or other person,
 - (b) The temporary or permanent serious deterioration of a patient's, user's or other person's state of health,
 - (c) A serious public health threat"
- (EU regulation 2017/745 MDR Article 2 (65))

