2.3 INTERVENTIONS

Included participants of all three groups receive a standardized skin cleansing regime consisting of cleansing of the skin with water and the addition of a mild cleansing product. Cleansing is done using disposable washing mitts. To remove possible residual stool from the skin, an additional skin oil can be used. After subsequent gentle drying of the skin, elastic disposable breathable incontinence pants are put on. This is considered as 'standard incontinence care'. In order to ensure the greatest possible standardization and uniformity, the same predefined products and procedures are used for all participants. The required products for the participants will be provided by the investigators and are listed in Table 1.

After baseline visits, included residents/patients will be randomly assigned on Day 0 to one of the following three study arms:

- **Study arm 1 (Experimental intervention I):** Standard incontinence care with additional daily topical application of a film-forming leave-on skin protectant (ESENTA™ Hautschutz Spray) that builds a protective layer on the surface of the skin
- **Study arm 2 (Experimental intervention II):** Standard incontinence care with additional daily topical application of a lipophilic leave-on skin protectant (Hydrophobes Basisgel DAC) that forms a hydrophobic physical barrier on the skin
- **Study arm 3 (Control group):** Standard incontinence care alone, no additional intervention in the control group

The interventions are described in detail according to the template for intervention description and replication (TIDieR) checklist [17] in Table 1. The items 10 and 12 do not apply for study protocols and are therefore not listed in the table [17].

Table 1: Description of interventions according to the template for intervention description and replication (TIDieR) [17].

Item	Experimental intervention I	Experimental intervention II	Control group
1. Brief name	Film-forming leave-on skin protectant for IAD prevention	Hydrophobic leave-on skin protectant for IAD prevention	No skin protectant

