2.1 Definitions

Intention-to-treat/Full analysis population

The full analysis set (FAS) contains all participants that met the inclusion criteria and were randomized, irrespective of possible protocol deviations, discontinuation of the study treatment or withdrawal from the study by the subject. Study participants will be categorized according to the intended treatment. As only exception, the following reasons cause an exclusion of participants from the full analysis set: (I) No treatment was applied at all or (II) there are no data available after the subject's randomization. Subjects excluded from the full analysis set will be mentioned in the study report and reasons for exclusion will be documented per group. In case of consent withdrawal, all subject's data collected until this time point will remain part of the study database and may not be removed.

Per protocol population

The per protocol (PP) set is defined as follows: (I) Participants that completed the study without major protocol deviations or violations (i. e. wrong product/incorrect application, missing application for more than 72 h, more than three missing study visits, inclusion/exclusion criteria not met) and (II) terminated the study regularly (study participation of at least 7 consecutive days).

For all subjects included in the full analysis set but not in the PP set, the reason for exclusion will be stated in the study report per group.

Safety analysis set

The safety population comprises all patients. Due to blinding, it doesn't matter whether they received one dose of the product or not.

Nr.	Inclusion criteria	Variable name	Comment
1	Geriatric patients or residents (≥ 65 years) staying/living in one of the participating institutions	sc_0080, sc_0091	sc_0091 for age; see sc_0020 at mnppid_visit for detailed info
2	Being incontinent of urine and stool	sc_0100	
3	Expected minimum length of stay of 14 days	sc_0110	
4	Intact skin with no clinical signs of IAD or intact skin with early clinical signs of IAD but without clinical signs of infection (GLOBIAD category 1 A)	sc_0121	Check sc_0122 for IAD category
5	Written informed consent	sc_0130	
Nr.	Exclusion criteria	Variable name	Comment/Analysis
1	Residents/patients at the end of life	sc_0140	
2	Residents/Patients with skin loss due to IAD (GLOBIAD category 2 A) and/or signs of clinical infection in the IAD area (GLOBIAD category 1 B or 2 B)	sc_0150	

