4.4.1 Safety/Tolerability

Events are defined according to the definition of the EU regulation 2017/745 Medical Device Regulation (MDR) Article 2 and will be checked regularly.

Adverse events

- Untoward medical occurrence, e.g. allergic reaction
- Unintended disease or injury
- Untoward clinical signs, e.g.: abnormal laboratory finding

Incidents

- any malfunction or deterioration in the characteristics or performance of the skin protectants

Serious adverse events / Serious incidents that (in-)directly lead to

- Death
- Serious deterioration in the health

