7.2.2 Safety/Tolerability

AEs, SAEs, incidents and serious incidents will be -if any occurred- listed per patient and for the total trial.

The safety analysis based on the safety analysis set (according to the patients' received treatment) includes calculation of frequencies and incidence rates as well as incidence rate ratios and corresponding 95% confidence intervals of adverse and serious adverse events using poisson regression or negative binomial regression models depending on the distribution of the variables.

Results of safety analysis will be interpreted and discussed thoroughly also for minor group differences, since statistical significance is not of importance here.

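### Protocol and SAP define adverse events differently; under the protocol's definition the planned rate ratios against control cannot be estimated, and the safety set's blinding rationale does not hold

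*Combined protocol and SAP*

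**What the plan says.** **Event definitions.** Protocol 5.3.1 says an AE is an untoward occurrence "in the context of the clinical investigation, and is related to the investigational device". The next definition builds on it: "Serious Adverse Event (SAE) means any AE that led to any of the following". SAP 4.4.1 refers to Article 2 of the same EU regulation, but its list of AEs opens with "Untoward medical occurrence, e.g. allergic reaction" and nowhere asks for relatedness.

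**Arms.** Protocol 2.3 describes arm 3 as "Standard incontinence care alone, no additional intervention in the control group". Arm 1 receives a film-forming spray with CE certification. Arm 2 receives a hydrophobic gel, of which Protocol 5.3 says "It may be regarded as a cosmetic product according to the EU Regulation No 1223/2009 on cosmetic products".

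**Safety analysis.** The protocol summary plans only to list events. SAP 7.2.2 goes further and plans "frequencies and incidence rates as well as incidence rate ratios and corresponding 95% confidence intervals of adverse and serious adverse events", from Poisson or negative binomial models, with participants grouped by the treatment they received.

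**Safety set.** SAP 2.1 reads "The safety population comprises all patients. Due to blinding" and goes on to say that it is immaterial whether a dose was received. Protocol 3.3 says "involved caregivers and participants will not be blinded".

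**The concern.** The analysis compares arms on a quantity that, under one of the two definitions in force, only some arms can produce. A participant given no protectant cannot have an event related to it. The control count would then be zero because of the definition, not because the arm is safer, and every event in a protectant arm would push the ratio towards harm. The trial exists to inform a confirmatory trial, and an artefact of this kind would mislead its safety planning. A fixed zero in one arm could also hint at the permuted arm labels to the blinded statistician.

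The safety-set wording raises a smaller problem. The reason given for including everyone does not fit an open-label intervention, and treating receipt as immaterial clashes with grouping by receipt. Someone allocated to a protectant who never had an application has no stated place: by treatment received, that person resembles a control participant.

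**Working it through.** The documents give no AE rate, rate ratio or power for safety, so there is no planned figure to reproduce. The check is whether the planned ratio can be estimated under each definition.

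**Inputs.** n = 70 per arm (Protocol 2.8.1; the 220 recruited according to SAP section 3 would be about 73 per arm, which changes nothing below). Event counts are not in the documents. I assume 4 or 7 related events per protectant arm, and an all-cause background of 10% to 30%, for illustration only. Person-time is taken as equal across arms.

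**1. Protocol definition, protectant versus control.** The Poisson estimate is log RR = log(x1/T1) − log(x0/T0), with SE = √(1/x1 + 1/x0). With x0 = 0 both are infinite. A negative binomial model has the same mean structure and the same problem. Fitting the Poisson model to counts of 7, 7 and 0 shows the divergence: log RR is 11.1 (SE 59) after 10 iterations and 26.1 (SE about 107,000) after 25.

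The exact conditional 95% interval for x events against 0 has lower limit p/(1 − p), with p = 0.025^(1/x), and no upper limit. For x = 7, p = 0.590 and the limit is 0.590/0.410 = 1.44.

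| Assumed events, protectant vs control | Exact 95% interval for the ratio |
|---|---|
| 4 vs 0 | 0.66 to infinity |
| 5 vs 0 | 0.92 to infinity |
| 6 vs 0 | 1.18 to infinity |
| 7 vs 0 | 1.44 to infinity |

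From six related events upward the interval lies wholly above 1, even if the true all-cause rates in the two arms are identical.

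**2. Protocol definition, arm 1 versus arm 2.** If both protectants count as the device, the ratio is estimable. For 7 vs 4: RR = 1.75, SE = √(1/7 + 1/4) = 0.627, 95% CI 0.51 to 5.98. If only the spray counts, arm 2 is also zero by construction and no contrast between arms is estimable.

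**3. No relatedness condition (SAP 4.4.1).** All untoward events count in every arm and the ratios are finite. With an assumed excess of 10 percentage points:

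| Background | Events | RR | 95% CI |
|---|---|---|---|
| 10% | 14 vs 7 | 2.00 | 0.81 to 4.96 |
| 20% | 21 vs 14 | 1.50 | 0.76 to 2.95 |
| 30% | 28 vs 21 | 1.33 | 0.76 to 2.35 |

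These are wide but interpretable.

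**4. Safety set.** SAP 2.1 rests inclusion on blinding; Protocol 3.3 denies blinding to those who apply and receive the product. SAP 2.1 says receipt does not matter; SAP 7.2.2 groups by it. Both pairs conflict.

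**The case against.** **The control zero is not established.** The SAP is the later document and governs the analysis, and its definition has no relatedness condition. Protocol Table 3 schedules AE recording at every visit for all arms. Protocol 5.3.1 does not follow its own definition: observation starts at consent, before any product is applied, and the text on medical treatment adds relatedness to the product as if it were an extra condition. This stands. A reader might infer that control events were in fact never recorded; the documents do not show that. They show two definitions and no statement of which one governed capture. SAP 4.4.1 does not settle it, since it points to the regulation the protocol also cites.

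**The restriction was deliberate.** Protocol 5.3.1 explains that this population has many concurrent illnesses. That supports a listing of related events, which is all the protocol summary planned. It does not support rate ratios against an arm without the product.

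**The gel may well count.** Protocol 5.3 treats the two protectants in parallel, 5.3.1 moves between device and product, and SAP 4.4.1 speaks of protectants in the plural. A reader might infer that only arm 1 can generate an AE; the texts leave this open.

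**Other safety data exist.** A reader might infer that the trial has no fair safety comparison at all. Local intolerances are assessed at all eight visits with no relatedness or arm condition (Protocol Table 2, SAP 4.2), and reasons for early termination are captured (SAP 4.1). What may be missing is a formal all-cause event count.

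**Some blinding is real.** The skin assessor, data manager and statistician are blinded, so it would be wrong to say that the trial has none. Including all patients in a safety set is not an error either; only the reason given, and the clash with grouping by receipt, are. Nor do the documents name who judges relatedness, so a claim that unblinded staff do so would be inference.

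**Conclusion.** The concern holds as an unreconciled contradiction with a definite consequence. If the protocol definition governed capture, the AE and SAE ratios of both protectant arms against control are not estimable, and any reported value or interval would reflect the definition and not the products. If the SAP list governed, the ratios are estimable but imprecise. The arm 1 versus arm 2 ratio is sound if both protectants count as the device. It would therefore go too far to call every planned ratio meaningless.

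The algebraic result does not depend on the assumed counts; the intervals shown do. I also assume that SAP 7.2.2 means comparisons with control: it names no contrasts, although SAP 7.2 lists all three pairs for the endpoints. Whether Protocol 5.3.1 renders the regulation correctly cannot be checked from these documents, and the sponsor should verify it.

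The safety-set rationale is wrong as written, but that is a matter of wording. The exploratory aim lowers the stakes without removing the problem, because these estimates are meant to feed a later trial.

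**What to change.** Recruitment is complete, so prospective recording cannot change. Amend the SAP before the safety tables are produced.

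1. Reconcile Protocol 5.3.1 with SAP 4.4.1, and state in the SAP which definition governed capture and whether events with the gel counted.
2. If all untoward events were captured in every arm, base the rate ratios on all-cause AEs and SAEs, and report relatedness as a separate attribute.
3. If only related events were captured, drop the AE and SAE ratios against control and say why. Report counts and exact rates per arm, marking the control zero as a product of the definition. Compare local intolerances, recorded deaths and early-termination reasons across all three arms.
4. Delete the blinding sentence in SAP 2.1. State one as-treated rule that agrees with SAP 7.2.2 and says where participants with no application are placed. Requiring at least one application is optional.

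The cost is SAP wording, a little more abstraction and analysis, and possibly the loss of the ratios against control.
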